Appendix 10 Systemic Lupus Erythematosus Disease Activity Index (SLEDAI-2K) (cont.)

This should be scored if any of the following conditions are present:

1. There is temporal thinning which is newly present for less than six months (if temporal alopecia is present for more than six months with no change it should not be counted)
2. Areas of scalp with total bald spots if present for less than six months (does not need to have accompanying discoid lesion or follicular plugging)
3. The presence of "lupus frizz" i.e., short of strands of unruly hair in the frontal or temporal area

If a patient complains of hair loss and there is nothing apparent on exam this descriptor is not scored.

MUCOSAL ULCERS:

Definition: Ongoing oral or nasal ulcerations due to active lupus.

An ulcer is scored if it is ongoing, it need not be new or recurrent. Ulcers can be present in either the nose or oral cavity. Erythema alone without frank ulceration is not sufficient to be scored, even if the erythema is present on the upper palate. Ulcers on the buccal mucosa and tongue are counted.

Mucosal ulcers are not counted as vasculitis.

PLEURISY

Definition: Classic and severe pleuritic chest pain or pleural rub with effusion or new pleural thickening due to lupus.

This descriptor is scored if the patient complains of pleuritic chest pain lasting greater than 12 hours. The pain should be classic, i.e., exacerbated by inspiration, to help distinguish it from musculoskeletal conditions such as costochondritis, which could be confused with pleurisy. The symptom must also be accompanied by objective findings.

PERICARDITIS:

Definition: Classic and severe pericardial pain with rub or effusion, or electrocardiogram or echocardiogram confirmation.

The symptom must be accompanied by objective findings.

Appendix 10 Systemic Lupus Erythematosus Disease Activity Index (SLEDAI-2K) (cont.)

LOW COMPLEMENT:

Definition: Decrease in CH50, C3 or C4 below the lower limit of normal for testing laboratory.

Exclude a low C4 or CH50 in patients with known inherited deficiency of C4.

INCREASED DNA BINDING

Definition: >25% binding by Farr assay or above normal range for testing laboratory.

FEVER:

Definition: >38°C. Exclude infectious cause.

This would be scored if one of the following conditions are present:

1. A documented temperature elevation >100.4°F or >38°C at the time of the visit.
2. A convincing history from the patient that she/he has been febrile within the preceding 10 days prior to the visit without any signs or symptoms suggestive of infection. Febrile is defined as above and not simply that the patient felt feverish. In this case the patient need not be febrile at the time of the visit for a score of 2 to be given.

As stated in the SLEDAI, fever secondary to infection is not to be scored although it is acknowledged that concomitant lupus activity and infection can occur. Fever in the presence of infection should only be scored on the SLEDAI if other evidence of lupus activity is present.

THROMBOCYTOPENIA:

Definition: <100,000 platelets/mm³.

LEUKOPENIA:

Definition: <3,000 white blood cells/mm³. Exclude drug causes.

This is exactly as described, WBC <3,000/mm³. The presence of an absolute lymphopenia does not count in the SLEDAI. A note of caution, do not confuse

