Appendix 9 BILAG-2004 Index Glossary (cont.)

REFERENCES

Rule of nines diagram. Burn Center, University of Utah Health Sciences Center
(<http://uuhsc.utah.edu/burncenter/emergencycare/extent.html>)

Appendix 10

Systemic Lupus Erythematosus Disease Activity Index 2000 (SLEDAI-2K)

(Circle in SLEDAI Score column if descriptor is present at the time of the visit or in the preceding 4 weeks.) (The same instrument can also be used going back only 10 days.)

Item no.	SLEDAI SCORE	Descriptor	Definition
1	8	Seizure	Recent onset, exclude metabolic, infectious or drug causes
2	8	Psychosis	Altered ability to function in normal activity due to severe disturbance in the perception of reality. Include hallucinations, incoherence, marked loose associations, impoverished thought content, marked illogical thinking, bizarre, disorganised, or catatonic behaviour. Exclude uraemia and drug causes
3	8	Organic brain syndrome	Altered mental function with impaired orientation, memory, or other intellectual function, with rapid onset and fluctuating clinical features, inability to sustain attention to environment, plus at least 2 of the following: perceptual disturbance, incoherent speech, insomnia or daytime drowsiness, or increased or decreased psychomotor activity. Exclude metabolic, infectious or drug causes
4	8	Visual disturbance	Retinal changes of SLE. Include cytoid bodies, retinal hemorrhages, serous exudates or hemorrhages in the choroid, or optic neuritis. Exclude hypertension, infection, or drug causes
5	8	Cranial nerve disorder	New onset of sensory or motor neuropathy involving cranial nerves
6	8	Lupus headache	Severe, persistent headache; may be migrainous, but must be non-responsive to narcotic analgesia THIS WOULD RARELY BE ATTRIBUTED TO SLE...ALMOST NEVER SCORED
7	8	CVA	New onset Cerebrovascular accident(s). Exclude arteriosclerosis
8	8	Vasculitis	Ulceration, gangrene, tender finger nodules, periungual infarction, splinter hemorrhages or biopsy or angiogram proof of vasculitis

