Appendix 10 Systemic Lupus Erythematosus Disease Activity Index (SLEDAI-2K) (cont.)

Item no.	SLEDAI SCORE	Descriptor	Definition
16	2	Alopecia	Abnormal, patchy or diffuse loss of hair
17	2	Mucosal ulcers	Oral or nasal ulcerations
18	2	Pleurisy	Pleuritic chest pain or pleural rub with effusion, or pleural thickening (requires objective evidence)
19	2	Pericarditis	Classic pericardial pain and/or rub, effusion with ECG or echocardiogram confirmation (requires an objective component)
20	2	Low complement	Decrease in CH50, C3 or C4 below lower limit of normal for testing laboratory
21	2	Increased DNA binding	Increased DNA binding above normal range for testing laboratory
22	1	Fever	> 38°C. Exclude infectious cause
23	1	Thrombocytopenia	< 100 x 10 ⁹ platelets/L, exclude drug causes
24	1	Leukopenia	< 3 x 10 ⁹ WBC/L, exclude drug causes

SCORE:

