Appendix 10 Systemic Lupus Erythematosus Disease Activity Index (SLEDAI-2K) (cont.)

GUIDELINES FOR USE OF SLEDAI-2K MODIFIED FOR ASSESSMENT OVER 28 DAYS: TO ASSESS DISEASE ACTIVITY

General guidelines for filling out the SLEDAI-2K:

- The main principle to keep in mind is that this instrument is intended to evaluate current lupus activity and not chronic damage, severity is accounted for in part by the "weightedness" of the scale.
- Points are given exactly as defined.
- A descriptor is either scored the exact points allotted or not scored, i.e. given a zero. Descriptors are scored only if they are present at the time of the physician encounter or in the preceding 28 days. Windows acceptable in a clinical trial are acceptable in scoring the SLEDAI. However, it is never acceptable to fill in gaps which cover activity over 2-3 months or more. The reason for this is that disease activity at the visit might have changed several times in such intervals and the recording of distant activity becomes meaningless.

Please note that in the original SLEDAI the disease activity being scored was meant to cover only a ten day period, the modification to 28 days is a more useful assessment for use in clinical trials, in order to capture disease activity between monthly visits.

- The descriptor must be documented by the notes written in the physician encounter form and generally applies to the clinical data and not to the laboratory data. The laboratory data is strictly defined as per cutoffs and documentation is provided by the reports from the commercial laboratory.
- Descriptors do not have to be new but can be. They can be ongoing, recurrent, or initial events. Each would be scored the same way. An example would be a malar rash or mucosal ulcer. In these situations a malar rash observed at the initial visit but which remains unchanged for the next six months, irrespective of any treatment, is scored 2 points each time the SLEDAI is completed. Since the nature of lupus is that manifestations are not usually fleeting it would be rare for descriptors to appear transiently during the month and not at the time of the encounter. This is discussed in more detail for each descriptor but is especially

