Appendix 10 Systemic Lupus Erythematosus Disease Activity Index (SLEDAI-2K) (cont.)

relevant for the neurologic (except for seizure or CVA), pulmonary, and cutaneous manifestations.

- In some descriptors the exclusions written may not be exhaustive. The intent of the SLEDAI is that the descriptor be attributed to SLE. If the physician does not attribute the descriptor to SLE it should not be scored, but full documentation must be provided.

Written in italics is the definition for each descriptor precisely provided in the SLEDAI SCORE

SEIZURE

Definition: Recent onset (last 28 days). Exclude metabolic, infectious or drug cause, or seizure due to past irreversible CNS damage.

This descriptor is scored if the patient has had a witnessed seizure or convincing description (such as tongue biting or incontinence) within 30 days of the current encounter. The patient need not have a positive EEG, CT scan, PET scan, QEEG, or MRI. The CSF may be totally normal.

A seizure is also not counted:

1. If a metabolic cause is determined.
2. In the presence of a proven infectious meningitis, brain abscess, or fungal foci.
3. If there is a history of recent head trauma.
4. In the presence of an offending drug.
5. In the presence of severe hyperthermia or hypothermia.
6. If the patient has stopped taking anticonvulsant medication.
7. If the patient has a documented sub-therapeutic anticonvulsant drug level.

PSYCHOSIS

Definition: Altered ability to function in normal activity due to severe disturbance in the perception of reality. Include hallucinations, incoherence, marked loose associations, impoverished thought content, marked illogical thinking, bizarre, disorganized, or catatonic behavior. Exclude uremia and drug causes.

This descriptor is scored if any of the criteria above are met.

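### Appendix 10's fever guide conflicts with the SLEDAI-2K form and general rules on weight (2 points against 1) and look-back (10 days against 28)

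*Combined protocol and SAP*

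**What the plan says.** **Weight.** Item 22 of the Appendix 10 form allots fever 1 point, with the definition "> 38°C. Exclude infectious cause". The guide's general rules leave no room for another value: "A descriptor is either scored the exact points allotted or not scored". The guide's fever entry lists two ways to score the item: a temperature documented at the visit, or a convincing history. Of the second it says: "In this case the patient need not be febrile at the time of the visit for a score of 2 to be given".

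**Look-back.** The form's header instructs: "Circle in SLEDAI Score column if descriptor is present at the time of the visit or in the preceding 4 weeks". Section 4.4.5.2 and the guide's general rules both give 28 days. The general rules also explain that a ten-day period belonged to the original SLEDAI and was lengthened to 28 days for trial use. The fever entry nevertheless requires that the patient "has been febrile within the preceding 10 days prior to the visit".

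**Use.** Section 4.4.6 defines SRI-4 response by three conditions at Week 48 compared with baseline, the first being a SLEDAI-2K reduction of at least 4 points. SRI-4 is the only secondary efficacy endpoint in Table 1.

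**A smaller item.** The guide's seizure entry gives 28 days in its definition line, then tells raters to score a seizure "within 30 days of the current encounter".

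**The concern.** Appendix 10 is the protocol's operational scoring text. A rater who turns to the fever entry finds a weight and a window that differ from the form being filled in. The entry produces two errors in opposite directions: a history-only fever on days 11 to 28 is left out (0 instead of 1), and one within 10 days is scored 2 instead of 1.

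History is also the limb that matters most in practice. After Week 12 the Schedule of Activities has SLEDAI-2K only at Weeks 24, 36, 48 and 56, so a fever between visits will mostly reach the rater through the patient's account. Section 4.4.5 prefers the same assessor at each visit but does not require it. Section 4.4.5.2 exempts investigators already trained for the parent study from retraining.

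At stake is the SLEDAI-2K component of SRI-4, which turns on a hard 4-point cutoff. One point is enough to move a patient who sits on it.

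**Working it through.** The plan states no figure to reproduce: Section 6.1 reports no formal sample size calculation. The check compares the texts and then works through the cutoff.

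**Step 1: the instructions side by side**

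| Source | Fever weight | Look-back |
|---|---|---|
| Form, item 22 and header | 1 | 4 weeks |
| Guide, general rules | exact form weight or zero | 28 days |
| Section 4.4.5.2 | not addressed | 28 days |
| Guide, fever entry (history) | 2 | 10 days |

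The fever entry stands alone on both counts. For a fever documented at the visit, the guide gives no separate weight, so the form's 1 point applies without conflict.

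**Step 2: size of the window difference**

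Days dropped = 28 − 10 = 18 (days 11 to 28). Share of the window = 18/28 = 64%. This applies only to fever known by history.

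**Step 3: effect on the 4-point component**

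Let R be the net reduction from baseline to Week 48 on all other items. The component is met if the total reduction is at least 4.

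| Fever pattern (by history) | Reduction by form | Reduction by fever entry | Result differs only at |
|---|---|---|---|
| Within 10 days, baseline only | R + 1 | R + 2 | R = 2 (3, not met; 4, met) |
| Within 10 days, Week 48 only | R − 1 | R − 2 | R = 5 (4, met; 3, not met) |
| Days 11–28, baseline only | R + 1 | R | R = 3 (4, met; 3, not met) |
| Days 11–28, Week 48 only | R − 1 | R | R = 4 (3, not met; 4, met) |

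If fever is present at both visits and scored alike, it cancels and nothing changes. If it is weighted 1 and then 2, the reduction is R − 1 and the result changes at R = 4. If 2 and then 1, it is R + 1 and the result changes at R = 3.

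Each pattern therefore has a single value of R at which classification changes, and the changes run in both directions.

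**Step 4: seizure**

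The 28-day and 30-day figures disagree only for an event on day 29 or 30. The item carries 8 points, so a discrepancy would change the component over a wide range (R from −4 to 3 if at baseline only, R from 4 to 11 if at Week 48 only), but the exposure is two days.

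**The case against.** **The weight is largely settled already.** Raters circle a preset value, and the general rules forbid any other. This stands. A reader might infer that the weight of fever is open in this trial; the form and the exact-points rule do not support that. What remains is an entry that tells the rater to break the rule.

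**The look-back is also mostly fixed, and a narrower limit might be deliberate.** Three places give 28 days or 4 weeks. The guide does set item-specific limits elsewhere, such as a minimum duration for pleurisy, so a shorter window for unwitnessed fever is conceivable. The form's header also notes: "The same instrument can also be used going back only 10 days". But nothing says that this trial uses that option for fever, and the guide's account of the ten-day period suggests leftover text. That origin is an inference.

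**Uniform use of the fever entry would still be consistent.** True: disagreement between raters or visits requires that some follow the entry and others the form. Uniform use would nonetheless depart from the 28-day instrument specified in Section 4.4.5.2.

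**Flares.** A reader might extend the point to the SELENA-SLEDAI Flare Index, which counts a SLEDAI rise of at least 3. The documents give little support. Appendix 11 already lists new or worse SLE fever as a mild or moderate flare item, and Section 4.4.5.2 excludes severe flares triggered by the score alone.

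**Seizure.** A reader might say that the guide contradicts the form here too. The form says only that onset is recent, under its 4-week header; the two numbers are both inside the guide. The general rules also accept trial visit windows in scoring, which softens a two-day gap.

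**A changed component is not a changed response.** SRI-4 also requires the BILAG-2004 and PGA conditions, and Section 4.2.2.3.4 makes patients on the listed escape therapies non-responders regardless. Training is planned as well. All of this stands and limits the effect.

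**Conclusion.** The fever entry is wrong as written on both weight and look-back, and following it mis-scores a history-only fever by 1 point in one direction or the other. The consequence is confined to patients whose other items leave them exactly at the 4-point cutoff, and to raters who follow the entry rather than the form.

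A reader might want to attach a percentage of SRI-4 outcomes. The documents give neither the frequency of SLE fever near an endpoint visit nor the share of patients at the cutoff, so any percentage would be invented. The share is probably very small. SRI-4 is secondary, efficacy is summarised without a formal sample size, and the primary safety objective is unaffected. This is a minor point, worth making because the correction is specific and nearly free.

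The conclusion assumes that the 28-day window in Section 4.4.5.2 is the intended one for every item, fever included. The sponsor's training materials are not among the documents and may already resolve the conflict.

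**What to change.** 1. Edit the fever entry in Appendix 10 to the form's 1 point and to a 28-day window for history.
2. Add one sentence to Appendix 10 stating that the form's weights and the 28-day window govern wherever a descriptor's guide text differs.
3. Send raters a short note with the correction, including those exempt from retraining.
4. As a minor tidy-up, align the two seizure windows inside the guide.

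The cost is a few lines of text in one appendix and one communication to sites. No assessment, visit, sample size or analysis changes.

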Appendix 10 Systemic Lupus Erythematosus Disease Activity Index (SLEDAI-2K) (cont.)

this WBC with that used to satisfy the ACR criteria for SLE which is WBC $<3,500/\text{mm}^3$.

With regard to current use of possible offending drugs, the following guidelines are to be considered:

1. The nadir after cyclophosphamide, i.e., low WBC at 10 days after receiving cyclophosphamide in a patient known to have a WBC $\geq 3,000$ at the time of receiving cyclophosphamide should not be counted.
2. Do not score leukopenia appearing after initiation of a new medication known to be associated with leukopenia, such as azathioprine or sulfa drugs. If the patient develops a WBC <3000 while taking drugs which may cause leukopenia, score this only if the dosage of medication is unchanged since the last WBC determination.

1. localized and generalized manifestations of acute cutaneous lupus erythematosus (malar rash, maculopapular rash, photosensitive rash, bullous lupus erythematosus);
2. subacute cutaneous lupus erythematosus (annular / polycyclic or papulosquamous / psoriasiform); and
3. chronic cutaneous lupus erythematosus (localized and generalized discoid lupus, verrucous/hyperkeratotic discoid lupus, mucosal discoid lupus, tumid lupus, perniosis/chilblain lupus, and lupus profundus/lupus panniculitis).

Training in the use of the CLASI will be provided to Investigators. Wherever possible, digital images of the lesions should be obtained.

Activity

Lesion activity is scored for 13 specified anatomical areas in terms of erythema (absent=0; pink or faint erythema=1; red=2; dark red, purple, violaceous, crusted, or hemorrhagic=3) and scale/hypertrophy (absent=0; scale=1; verrucous or hypertrophic=2). The severity score for each area is based on the worst lesion within that area.

The patient is asked about mucous membrane involvement, and if this is reported, the affected areas are examined (absent=0, present=1).

The patient is asked about hair loss in the past 30 days (patient-reported absence=0, presence=1). Non-scarring alopecia on examination is scored by examining the scalp in quadrants (absent=0; diffuse, non-inflammatory=1; focal or patchy in one quadrant=2; focal or patchy in more than one quadrant=3). The scores for the various anatomical areas are summed.

The maximum possible score for the Activity component of the CLASI is 70.

Appendix 12 Cutaneous Lupus Erythematosus Disease Area and Severity Index (CLASI) (cont.)

Damage

Skin damage is scored for 12 specified anatomical areas (as for the Activity score but excluding the scalp, which is scored separately; see below). Damage in each area is scored for dyspigmentation (absent=0; present=1) and for scarring, atrophy, and panniculitis (absent=0; scarring=1; severe atrophic scarring or panniculitis=2). As for the Activity component of the index, the damage severity score for each area is based on the worst lesion within that area. The scores for the various anatomical areas are then summed.

The patient is asked whether the dyspigmented cutaneous lesions usually remain visible for more than 12 months. If so, this is taken to indicate that the lesions are permanent, and the dyspigmentation score is doubled.

The scalp is examined for scarring, again by dividing into quadrants (absent=0; scarring in one quadrant=3; two quadrants=4; three quadrants=5; whole skull scarred=6).

The maximum possible score for the Damage component of the CLASI is 56.

REFERENCE

Appendix 12 Cutaneous Lupus Erythematosus Disease Area and Severity Index (CLASI) (cont.)

Cutaneous LE Disease Area and Severity Index (CLASI)

[figure not shown]
Select the score in each anatomical location that describes the most severely affected cutaneous lupus-associated lesion

activity			damage		
Anatomical Location	Erythema	Scale/ Hypertrophy	Dyspigmentation	Scarring/ Atrophy/ Panniculitis	Anatomical Location
	0-absent 1-pink; faint erythema 2- red; 3-dark red; purple/violaceous/ crusted/ hemorrhagic	0-absent; 1-scale 2- verrucous/ hypertrophic	0-absent, 1-dyspigmentation	0 – absent 1 – scarring 2 – severely atrophic scarring or panniculitis	
Scalp				See below	Scalp
Ears					Ears
Nose (incl. malar area)					Nose (incl. malar area)
Rest of the face					Rest of the face
V-area neck (frontal)					V-area neck (frontal)
Post. Neck &/or shoulders					Post. Neck &/or shoulders
Chest					Chest
Abdomen					Abdomen
Back, buttocks					Back, buttocks
Arms					Arms
Hands					Hands
Legs					Legs
Feet					Feet

Mucous membrane

Mucous membrane lesions (examine if patient confirms involvement) 0-absent; 1-lesion or ulceration	Dyspigmentation Report duration of dyspigmentation after active lesions have resolved (verbal report by patient – tick appropriate box)  Dyspigmentation usually lasts less than 12 months (dyspigmentation score above remains)  Dyspigmentation usually lasts at least 12 months (dyspigmentation score is doubled)
--	---

Alopecia

Recent Hair loss (within the last 30 days / as reported by patient) 1-Yes 0-No	 
NB: if scarring and non-scarring aspects seem to coexist in one lesion, please score both

Divide the scalp into four quadrants as shown. The dividing line between right and left is the midline. The dividing line between frontal and occipital is the line connecting the highest points of the ear lobe. A quadrant is considered affected if there is a lesion within the quadrant.	
Alopecia (clinically not obviously scarred) 0-absent 1-diffuse; non-inflammatory 2-focal or patchy in one quadrant; 3-focal or patchy in more than one quadrant	Scarring of the scalp (judged clinically) 0- absent 3- in one quadrant 4- two quadrants 5- three quadrants 6- affects the whole skull

Total Activity Score
(For the activity score please add up the scores of the left side i.e. for Erythema, Scale/Hypertrophy, Mucous membrane involvement and Alopecia)

Total Damage Score
(For the damage score, please add up the scores of the right side, i.e. for Dyspigmentation, Scarring/Atrophy/Panniculitis and Scarring of the Scalp)

Appendix 13

Physician's Global Assessment

The investigator's global assessment of the patient's current disease activity (using Physician's Global Assessment [PGA]) will be marked on a 100-mm horizontal visual analogue scale marked from "none" to "severe" and graded from 0 to 3 (see example that follows). The investigator should refer to assessments at prior visits and move the tick mark according to his or her assessment of the patient's disease activity over the preceding 28 days. The PGA should be done after the investigator has done the clinical history and examination of the patient and has completed the British Isles Lupus Assessment Group, the Safety of Estrogens in Lupus Erythematosus National Assessment, the Systemic Lupus Erythematosus Disease Activity Index, and (where appropriate) the Cutaneous Lupus Erythematosus Disease Area and Severity Index and 28-joint counts.

Pertinent laboratory values should be taken into account before completing the PGA rating. If relevant laboratory results are pending, the investigator may make a provisional marking on a local paper copy of the PGA case record form and finalize the assessment when all pertinent data is available.

**Appendix 13
Physician's Global Assessment (cont.)**

PHYSICIAN'S GLOBAL ASSESSMENT

[figure not shown]
Check if assessment was not done

Date of Assessment: — - — - —
 Mo Day Year

Please answer the following questions by placing a **vertical mark through the line**

Global Assessment of Disease Activity

On the line below, where would you rate the subject's SLE over the past 28 days?

Rater Initials:

--	--	--

Do not photocopy the document as this is NOT to scale

